7.2 Handling of Dropouts or Missing Data

Missing observations will be treated as missing at random, and Missing data will not be imputed.

7.3 Multicenter Studies

For Part A, B and C, this is a monocenter study. For Part D, E and D Extension, this is a multicenter study. For the purpose of PK and safety analysis data across sites will be pooled together and presented per dose group.

7.4 Examination of Subgroups

For Parts D, E and D Extension, blood galactitol changes will be analyzed based on below subgroup categories if data permit:

- Gender: Male / Female
- Age: $\langle 21 \text{ years} / \rangle = 21 \text{ years and } \langle 30 \text{ years} / \rangle = 30 \text{ years}$
- BMI: $<22 \text{ kg/m}^2 / 22-25 \text{ kg/m}^2 / >25 \text{ kg/m}^2$
- Enzyme activity: <0.1%, 0.1-0.4%, >0.4%

Additionally forest plot will be displayed for Part D and E at Day 32 and for Part D extension at Day 90/EOT for blood galactitol results.

7.5 Analysis Populations

Two analysis populations will be defined:

• Screened Population (SP): The screened population will consist of all subjects who are screened independent if they were eligible or not.

- Randomized Population: The randomized population will consist of all subjects who are randomized to any cohort.
- Safety Population: The safety population will consist of all subjects who are randomized and receive at least 1 dose of study drug. All analyses will be performed according to treatment received. This population will be used for all analyses of safety data and biomarker data.
- Pharmacokinetic Population: The PK population will consist of all subjects who receive at least 1 dose of AT-007 and have sufficient concentration-time data to estimate at least one of the planned PK parameters, as determined by the study Pharmacokineticist. This population will be used for all analyses of PK.

For Parts D and E, the safety and PK population may be defined separately for the SAD and MAD periods.

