The SRC will make recommendations to the Sponsor regarding dose escalation or de-escalation for each cohort based on the results from the previous cohort as described in [Section 3.4](#). The Sponsor will act upon this recommendation and inform the Investigator(s) and the IRB(s)/IEC(s).

The SRC will pay particular attention to DLTs defined as any AT-007-related AE or clinically relevant finding on laboratory tests, ECGs, vital signs, or physical examinations that, in the opinion of the Investigator and/or the SRC, precludes administering the dose to any subject and/or continuing to administer daily doses to the subject who experienced the event. Specific individual subject-level dose stopping criteria for hepatic and renal toxicity are described in [Appendix G](#) and [Appendix H](#). For DLTs, as well as fatal serious adverse events (SAEs) and life-threatening SAEs, breaking the blind will be considered and initiated (as needed) per SRC discussion and agreement.

Dose-escalation will be stopped and de-escalation initiated if:

- ≥ 2 subjects on AT-007 (B and C cohorts of the same dose level considered together) experience a DLT at any time through 24 hours after the last dose of study treatment
- Any subject on AT-007 has a fatal SAE or life-threatening SAE requiring urgent intervention at any time through 24 hours of the last dose of study treatment

The maximum tolerated dose (MTD) will be the dose level below the dose level at which one or more of the events listed above occurs.

Dose escalation within each part of the study will continue until the MTD is identified per the rules described earlier in this section or the SRC and/or Sponsor decide to stop dose escalation. Dose de-escalation, if initiated within any part of the study, will continue until the MTD is identified or the SRC and/or Sponsor decide to stop.

If the events outlined in the above MTD definition do not occur at any dose level in a study part, then the MTD will be the highest dose level in that study part.

If the events outlined in the above MTD definition occur at any given dose level, the Sponsor may decide to investigate a dose higher than the previously well-tolerated dose but lower than the dose at which one of the events outlined in the above MTD definition occurred.

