6.6. Day 1 through Penultimate Visit (Part C, Days 1 through 9)

Exact time points and allowable windows for assessments and sample collection are provided in the Schedule of Assessments ([Appendix C](#)).

The visit schedule for subjects in Part C is identical to that for subjects in Part B with the following exceptions:

- No randomization. All subjects will receive open-label AT-007.
- Subjects will have a lumbar puncture on Day 7 (see [Appendix C](#) for notes on timing of the lumbar puncture relative to the last dose of study drug).

6.7. Day 1 through Penultimate Visit (Parts D and E, Days 1 through 34)

Exact time points and allowable windows for assessments and sample collection are provided in the Schedule of Assessments for Part D ([Appendix D](#)) and Part E ([Appendix E](#)).

Subjects will have 3 in-clinic stays.

- Subjects will remain at the CRU from Check-in on the morning of Day -1 until Discharge on Day 3 (Cohorts D1 and D2 and Part E) or Day 4 (Cohort D3).
- Subjects will remain at the CRU from Check-in on the morning of Day 12 until Discharge on Day 13.
- Subjects will remain at the CRU from Check-in on the morning of Day 32 until Discharge on Day 34.

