- d: Vital signs will be measured at Screening, check-in on Days -1 and 6, predose (within 60 min before the dose) on Days 1 and 7, at 4 hours (± 10 minutes) after the dose on Days 1 and 7, once daily on Days 2, 8, and 9, and at the EOS visit.
- e: Electrocardiograms will be performed at Screening, Day -1 check-in, predose (within 60 min before the dose) on Days 1 and 7, at 2 hours (± 10 minutes) after the dose on Days 1 and 7, and at the EOS visit.
- f: Samples for clinical safety laboratory tests will be collected under fasting conditions.
- g: Serum pregnancy tests at Screening, Day -1, and EOS visits; urine pregnancy tests at other time points. Also, female subjects claiming postmenopausal status will have that status verified with an FSH test at Screening. Once a female subject is verified as postmenopausal or otherwise not of childbearing potential, the subject is exempt for further pregnancy tests. On Day 6, the urine pregnancy test must be done (and the result negative) before study drug is administered.
- h: All doses of study drug will be administered at the clinic.
- i: On Day 1, blood samples for PK will be collected predose (within 60 minutes before the dose) and at 0.5, 1, 1.5, 2, 4, 6, 8, and 12 hours (± 5 minutes for all time points) after the dose. On Day 2, blood samples for PK will be collected predose (i.e., at 24 hours ± 5 minutes after the Day 1 dose and before the Day 2 dose). On Day 7, blood samples for PK will be collected predose (within 60 minutes before the dose) and at 0.5, 1, 1.5, 2, 4, 6, 8, and 12 hours (± 5 minutes for all time points) after the dose. Also, blood samples for PK will be collected at 24, 36, and 48 hours (± 5 minutes for all time points) after the Day 7 dose; these collections will be taken on Day 8 and Day 9.
- j: A lumbar puncture will be done after the Day 7 dose to collect CSF for analysis of AT-007. For Cohort C1, the timing (hours after the dose) of the lumbar puncture was based on PK results from Cohorts B1 and B2. For Cohort C2, the timing of the lumbar puncture was based on PK results from Cohorts B1, B2, and B3. For Cohort C2, the timing of the lumbar puncture will be based on PK results from Cohorts B1, B2, B3, and B4. The intent is to perform the lumbar puncture at the time of maximum observed concentration (T_{max}) after the Day 7 dose.

Note: The Schedule for Part C will differ from that for Part B only by the lack of randomization on Day 1 and the addition of a Day 7 lumbar puncture.

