2.4 Primary Endpoints

The primary endpoints of this study are overall safety and adverse events (AEs). Safety will be assessed by the following endpoints:

- AEs
- Clinical safety laboratory tests (hematology, chemistry, urinalysis)
- Physical examinations
- Vital signs
- Electrocardiograms (ECGs)

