3.1.3 Randomization and Treatment Assignments

Subjects will be randomly assigned to either AT-007 or matching placebo in Parts A, B, D, E and D Extension. The number of subjects to be treated with AT-007 and the number of subjects to be treated with placebo in each cohort are described in Section 3.1.4. Subjects will be assigned to open-label AT-007 in Part C.

Up to 116 subjects are planned to be dosed in this study:

- Part A: 5 cohorts of 8 healthy subjects each
- Part B: 2 cohorts of 6 healthy subjects each and 2 cohorts of 8 healthy subjects each
- Part C: 3 cohorts of 4 healthy subjects each
- Part D: 3 cohorts of 6 subjects with CG each
- Part E: 1 to 3 cohorts of 6 subjects with GALK-deficient Galactosemia each
- Part D Extension: 1 to 2 cohorts with a combined total of 16 subjects with CG

The number of cohorts and total number of subjects may increase if doses above 40 mg/kg are tested in additional cohorts.

In Parts A, B, D, E and D Extension, subjects will be randomized to receive either active drug (AT-007) or placebo. Each subject will receive an assigned treatment based on the randomization schedule prepared by the study statistician.

Parts A and B will be double-blinded (the Sponsor/ CRO, clinical site staff [except for unblinded pharmacist for Parts A and B], and the subjects will not know which subjects are treated with AT-007 or placebo).

In Part C, all subjects will be assigned to receive active drug (AT-007). Part C will be open-label.

In Parts D, E and D Extension the clinical site staff [except for the unblinded pharmacist], and the subjects will be blinded to study treatment. The Sponsor/CRO will not be blinded to study treatment in Part D, as the relationship between exposure in Parts D, E and D Extension (subject with galactosemia) vs. exposure in healthy subjects will need to be evaluated on an ongoing basis to ensure that AT007 blood level remain within the limits achieved in Part B. This process will minimize the number of subjects with galactosemia potentially exposed to plasma concentrations of AT-007 not previously tested and shown to be safe in healthy subjects.

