| Table 14.3.4.3c | Shift from Baseline in Clinical Laboratory Results – Part B and Part C cohorts combined (Safety Population) Shift from Baseline in Clinical Laboratory Results – Part D (Safety |
| Table 14.3.4.3d | Population) |
| Table 14.3.4.3de | Shift from Baseline in Clinical Laboratory Results – Part D Extension (Safety Population) Shift from Baseline in Clinical Laboratory Results – Part E (Safety |
| Table 14.3.4.3e Section 14.3.5 | Population) Additional Safety Data Summaries |
| Table 14.3.5.1a | Absolute and Change from Baseline Vital Signs by Visits – Part A (Safety Population) |
| Table 14.3.5.1b | Absolute and Change from Baseline Vital Signs by Visits – Part B and Part C (Safety Population) |
| Table 14.3.5.1c | Absolute and Change from Baseline Vital Signs by Visits – Part B and Part C cohorts combined (Safety Population) Absolute and Change from Baseline Vital Signs by Visits – Part D (Safety Population) |
| Table 14.3.5.1d | (Safety Population) Absolute and Change from Populing Vital Signs by Visits - Port D |
| Table 14.3.5.1de | Absolute and Change from Baseline Vital Signs by Visits – Part D Extension (Safety Population) Absolute and Change from Baseline Vital Signs by Visits – Part E |
| Table 14.3.5.1e | (Safety Population) |
| Table 14.3.5.2a | Summary of Observed Values and Change from Baseline for Continuous ECG Data – Part A (Safety Population) |
| Table 14.3.5.2b | Summary of Observed Values and Change from Baseline for Continuous ECG Data – Part B and Part C (Safety Population) Summary of Observed Values and Change from Baseline for Continuous ECG Data – Part B and Part C cohorts combined (Safety |
| Table 14.3.5.2c | Population) |
| Table 14.3.5.2d | Summary of Observed Values and Change from Baseline for Continuous ECG Data – Part D (Safety Population) |
| Table 14.3.5.2de | Summary of Observed Values and Change from Baseline for Continuous ECG Data – Part D Extension (Safety Population) |
| Table 14.3.5.2e | Summary of Observed Values and Change from Baseline for Continuous ECG Data – Part E (Safety Population) |

| Listing/Figure Number | Listing/Figure Name |
|--------------------------|--|
| Section 16.1.7 | Randomization |
| Listing 16.1.7.1a | Randomization Allocation – Part A (Safety Population) |
| Listing 16.1.7.1b | Randomization Allocation – Part B (Safety Population) |
| Listing 16.1.7.1c | Randomization Allocation – Part C (Safety Population) |

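### The Safety Population requires randomization, but Part C is not randomized, so applied as written it drops all 12 planned Part C subjects from the primary safety analysis

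*SAP*

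**What the plan says.** SAP 7.5 and Protocol 9.2.2 define the Safety Population in identical words: "The safety population will consist of all subjects who are randomized and receive at least 1 dose of study drug". Both apply it to every safety analysis; the SAP adds biomarkers ("This population will be used for all analyses of safety data and biomarker data"). SAP 2.4 makes overall safety and adverse events the primary endpoints.

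Part C has no randomization. Protocol 6.6 lists this as a difference from Part B: "No randomization. All subjects will receive open-label AT-007". The note to Protocol Appendix C agrees: "The Schedule for Part C will differ from that for Part B only by the lack of randomization on Day 1". SAP 3.1.3 states: "Subjects will be assigned to open-label AT-007 in Part C". The lists of randomized parts in Protocol Section 5 and SAP 3.1.3 name A, B, D, E and D Extension, and leave out C.

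The SAP nevertheless plans Part C safety output. SAP 7.12.1 names Part C among the parts to be summarised. Section 8 places the Part B and C tables, the combined B and C tables, and the Part C listings of adverse events and serious adverse events on the Safety Population. Tables 14.1.2b and 14.1.2c, which summarise the analysis populations for Parts B and C, are on the Randomized Population. Listing 16.1.7.1c is a randomization-allocation listing for Part C.

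**The concern.** Membership of the Safety Population needs two things, randomization and a dose, and Part C subjects have only the second. They fail the SAP's Randomized Population for the same reason. A programmer who follows SAP 7.5 literally would produce combined B and C tables containing Part B only, and empty Part C columns and listings.

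Two consequences matter. First, the healthy-volunteer multiple-dose safety data would be thinned at every dose above 5 mg/kg, including 40 mg/kg, the highest planned. Second, lumbar puncture is done only in Part C, so adverse events linked to it would appear in no safety summary.

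If a programmer instead includes Part C without comment, the primary safety analysis departs from its prespecified population with no record of the change.

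**Working it through.** **Inputs (planned numbers).** Part A: 5 cohorts of 8, with 6 on AT-007 in each (SAP Table 3-2). Part B on AT-007: 6, 4, 6 and 4 at 5, 10, 20 and 40 mg/kg, with 2 placebo per cohort (SAP Table 3-3). Part C: 4 on AT-007 at each of 10, 20 and 40 mg/kg (SAP Table 3-4).

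**The plan's own totals reproduce.** Part C: 3 × 4 = 12. Part B: 8 + 6 + 8 + 6 = 28. Parts B and C: 28 + 12 = 40, as in SAP 7.13. Healthy subjects: 40 + 28 + 12 = 80, as in the Protocol synopsis.

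**Definition applied literally.** Part C subjects randomized: 0. Part C subjects in the Safety Population: 0 of 12.

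| Set | With Part C | As written | Lost |
|---|---|---|---|
| All healthy subjects | 80 | 68 | 12/80 = 15% |
| Parts B and C, all | 40 | 28 | 12/40 = 30% |
| Healthy, on AT-007 | 30 + 20 + 12 = 62 | 50 | 12/62 = 19.4% |
| Healthy, multiple-dose AT-007 | 20 + 12 = 32 | 20 | 12/32 = 37.5% |

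By dose, healthy multiple-dose AT-007:

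| Dose (mg/kg) | With Part C | As written |
|---|---|---|
| 5 | 6 | 6 |
| 10 | 4 + 4 = 8 | 4 |
| 20 | 6 + 4 = 10 | 6 |
| 40 | 4 + 4 = 8 | 4 |

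The note to SAP Table 3-3 says the Part B cohort sizes were chosen to give at least 6 subjects on AT-007 at each well-tolerated dose, counting Part C. With Part C, every level meets that minimum. As written, 10 and 40 mg/kg have 4 each and miss it.

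**What the loss means for detecting events.** The documents give no adverse event rate, so this is an illustration over assumed rates p. The chance of seeing at least one event among n subjects is 1 − (1 − p)^n. At 10 or 40 mg/kg:

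- p = 5%: 1 − 0.95^8 = 33.7% with Part C; 1 − 0.95^4 = 18.5% as written.
- p = 10%: 1 − 0.9^8 = 57.0%; 1 − 0.9^4 = 34.4%.
- p = 20%: 1 − 0.8^8 = 83.2%; 1 − 0.8^4 = 59.0%.

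If no subject on multiple-dose AT-007 had a given event, the one-sided 95% upper bound on its rate is 1 − 0.05^(1/n). This is 8.9% for n = 32 and 13.9% for n = 20.

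**The case against.** The strongest reply is that intent is clear. SAP 7.12.1 and Section 8 prespecify Part C safety output, and a plan would not schedule listings that are empty by design. The documents also use the word loosely: the general design text (Protocol 3.1, SAP 3.1) says subjects in all parts are randomized on Day 1, and Section 8 plans an allocation listing for Part C. This supports calling the problem a drafting error. It does not make Part C randomized, because the specific statements in Protocol 6.6, Appendix C and SAP 3.1.3 outrank a general sentence. Nor does a table title override the definition of the population it names.

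Three further points stand and limit the harm:

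- **Dose escalation is unaffected.** The stopping rule in Protocol 3.5 counts dose-limiting toxicities with "B and C cohorts of the same dose level considered together", and the Safety Review Committee's review is not tied to any analysis population. The rule shows only that Part C was meant to count alongside Part B.
- **Part C data would not vanish.** SAP 7.1 requires all case report form data to be listed, and the adverse event term-mapping listings for Parts B and C (16.2.7.2b and c) carry no population restriction. What is lost is the summaries and the listings titled for the Safety Population.
- **Other results are untouched.** Safety output is descriptive and presented by part, so Parts A, D, E and D Extension do not change. Part C pharmacokinetic and cerebrospinal fluid summaries use the PK Population, which does not require randomization.

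**Conclusion.** The concern holds. The definition is wrong for one of the six parts, in both documents, for the primary endpoint. Applied as written, it excludes all 12 planned Part C subjects, halves the numbers on multiple-dose AT-007 in healthy subjects at 10 and 40 mg/kg, and breaks the plan's own minimum of 6 at those two doses. The size is conditional on literal application and on planned enrolment; actual numbers are not in the documents. The planned outputs make an intended exclusion implausible, so the realistic risk is either a programming error or an undocumented departure from the prespecified population. It should be corrected, but it does not call the design or the escalation decisions into question.

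**What to change.** In SAP 7.5 and Protocol 9.2.2, define the Safety Population as every subject who takes at least one dose of study drug, analysed by treatment received (the second half is already in both definitions). For Part C, replace the Randomized Population with all subjects assigned to treatment. Retitle Tables 14.1.2b and 14.1.2c accordingly, and make Listing 16.1.7.1c a treatment-assignment listing.

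Planned membership of the other parts does not change: in A, B, D, E and D Extension, randomization comes before the first dose on Day 1 (Protocol 6.4.1, 6.5.1, 6.7.1 and 6.8.1). The dosing-based wording also matches how the PK Population is already built.

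The cost is one sentence in each document and a few titles. Because Protocol 9.2.2 is protocol text, the SAP can be corrected first and the change recorded in SAP Section 4, which already lists departures from the protocol.

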7.6 Subject Accountability

Summaries of analysis populations and subject disposition will be presented by parts and will contain the following information:

- Number and percentage of subjects screened and screened failure
- Number and percentage of subjects enrolled
- Number and percentage of subjects randomized
- Number and percent of subjects who are dosed
- Number and percent of subjects who completed the study
- Number and percent of subjects who discontinued from study early and reason for early discontinuation
- Number and percent of subjects in each population

Subject disposition will be presented in listings using screened population.

7.7 Drug Exposure and Compliance

A data listing, by subject, containing study drug dosing and dosing errors, if any, will be provided.

For Parts D, E and D Extension, summary of compliance, including compliance categories of less than 80%, between 80% and 120%, and greater than 120%, will be reported by treatment group and study parts based on Safety Population. Compliance data will also be listed by study participants for each Part and Cohort.

7.8 Protocol Deviation Reporting

Important protocol deviations (IPD) will be identified and classified by the deviation types in the IPD document.

A listing of all IPDs identified will be presented for all subjects based on the safety population (SP) and will include the deviation type and description.

7.9 Subject Demographics and Baseline Characteristics

Demographic and baseline characteristics (including age, sex, race, ethnicity, weight, height, and body mass index) will be summarized using descriptive statistics by parts and cohorts based on safety population. Also disease characteristics will be summarized i.e. Blood Galactitol, Urine Galactitol, Blood Galactose, Blood GAL-1P, Blood Galactonate and Brain galactitol (MRS) for Part D, D extension and Part E. No formal statistical analyses will be performed.

The medical history of all subjects as well as the neurological history of subjects with CG and subjects with GALK-deficient Galactosemia will be coded by system organ class (SOC) and preferred term (PT) using the Medical Dictionary for Regulatory Activities (MedDRA) version 22.0 or higher. The number and percentage of subjects with abnormal findings in each SOC and each PT will be summarized by parts and cohorts based on safety population.

7.10 Analysis of Pharmacokinetic Data

Plasma and urine PK parameters of AT-007 (including metabolites if determined) will be summarized by dose level and part using descriptive statistics. CSF concentration of AT-007 for cohort C1, C2 and C3 will be summarized by Cohort.

The PK Population will be used for all listings, concentration summaries, PK summaries and statistical analysis. The individual sampling and subject concentration-time for plasma and CSF concentrations will be listed and displayed graphically (plasma only) on linear and semi-log scales. The plasma and CSF drug concentrations will be summarized descriptively by nominal time point, Part and Cohort in tabular and graphical (plasma only) formats (linear and semi-log scales). The amount of AT-007 in urine will be listed by subject and summarized by nominal collection interval, Part and Cohort. Summary statistics will include: n, arithmetic mean, standard deviation (SD), coefficient of variation (CV%), median, minimum, maximum, and geometric mean (GM).

Pharmacokinetic parameters for AT-007 will be listed and summarized descriptively by Part, Cohort and Day, including n, arithmetic mean, SD, minimum, median, maximum, CV(%),GM, geometric SD, geometric CV%; geometric CV% calculated as the square root of the exponentiated SD of the natural log transformed data (SQRT(exp(sln^2)-1)), where appropriate. For t_{max} , only n, minimum, median, and maximum will be reported.

The dose proportionality of the primary PK parameters, AUC_{last} , AUC_{inf} and C_{max} after single dose (Part A, Part D and E, single dose portion) and AUC_{tau} , and C_{max} for single and multiple doses, over the administered dose range will be investigated using the following power model,

log(PK parameter) = a + b * log(dose), where a is the intercept and b is the slope.

Dose proportionality will be assessed for each part of the study separately. Furthermore, pooling of data across all parts at same dose level may be used to access overall dose proportionality for the entire range of the administered doses. However, pooling will be based on either the Day 1 dose or following multiple doses.

Each log-transformed PK parameter will be fit with a power model with a fixed effect term for log-transformed dose. For each PK parameter, the slope and associated 90% CI will be presented. A minimum of 3 values per dose cohort must be available for a given parameter to estimate dose proportionality with the power model.

The following is the example SAS code can be implemented:

```
PROC MIXED DATA=PKPARM;
    BY PARAMCD;
    MODEL LOGPK= LOGDOSE / SOLUTION CL DDFM=KR;
    ESTIMATE "SLOPE" LOGDOSE 1 / ALPHA = 0.1 CL;
    ESTIMATE "INTERCEPT" INTERCEPT 1 / ALPHA = 0.1 CL;
    ODS OUTPUT SOLUTIONF =SOLNF;
    ODS OUTPUT ESTIMATES =ESTIMATE;
RUN;
```

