3.5. Dose Escalation/De-escalation

For Parts A, B, and C of the study (healthy subjects), safety and drug exposure will determine escalation or de-escalation. If the initial dose tested in Part A had not been well tolerated, the Sponsor may have chosen to de-escalate until a well-tolerated dose was identified. A careful analysis of available safety, laboratory evaluation, and drug PK data in healthy subjects was done to determine the starting dose for Part D in subjects with CG. A careful analysis of available safety, laboratory evaluation, and drug PK data in subjects with CG will determine the starting dose for Part E in subjects with GALK-deficient Galactosemia. The starting dose in Part E will not be higher than the highest acceptable dose used in Part D at the time of starting Part E. The starting dose in Part D Extension will be 20 mg/kg based on acceptable SAD and MAD safety and PK data from Cohort D2.

For Part D of the study (subjects with CG), safety, drug exposure, and biomarker analysis of galactitol will determine escalation or de-escalation. If the drug exposure in subjects with CG is similar to that seen in healthy subjects in Part A, the same or similar approach to dose escalation may be utilized. If there is any concern of altered drug exposure or drug clearance based on PK analysis after the single dose in the initial cohort of Part D, then alternative dose escalation to lower levels may be selected until the relationship between dose and exposure in subjects with CG is determined. Dose escalation may be stopped if an effect on galactitol (reduction in galactitol) is achieved, but it becomes apparent that higher drug exposure is not increasing reduction of galactitol or providing any additional benefit. If any tested dose is not well tolerated

while markedly reducing galactitol levels, lower dose levels may be tested until no/minimal reduction in galactitol levels is detected.

In case of multiple cohorts in Parts E, the dose escalation process will be the same as for Part D.

A second cohort of the Part D Extension (DE2) may be initiated to evaluate a dose higher than 20 mg/kg/day if this dose was well tolerated in the SAD and MAD portions of the study in both healthy volunteers and subjects with CG.

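### The optional power model pooled across all parts has no population term, so a patient–healthy exposure difference can bias the slope or widen its 90% CI

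*SAP*

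**What the plan says.** SAP 7.10 makes the by-part analysis the plan: "Dose proportionality will be assessed for each part of the study separately". It then permits, without requiring, a pooled fit: "pooling of data across all parts at same dose level may be used to access overall dose proportionality for the entire range". Day 1 and multiple-dose data are kept apart in that pool.

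The model is "log(PK parameter) = a + b * log(dose), where a is the intercept and b is the slope", and each parameter is "fit with a power model with a fixed effect term for log-transformed dose". The example code agrees: "MODEL LOGPK= LOGDOSE / SOLUTION CL DDFM=KR", with no CLASS, RANDOM or REPEATED statement. For reporting, "the slope and associated 90% CI will be presented". No limits for declaring proportionality are set.

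The dose-proportionality tables listed in SAP section 8 (14.2.6a to 14.2.6e2) are by part, except that B and C, both healthy, are combined.

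**The concern.** A pooled fit with one intercept assumes that patients and healthy subjects have the same exposure at the same mg/kg dose. The protocol does not assume this. Section 3.5 provides for "any concern of altered drug exposure or drug clearance" in CG, and section 5.2 keeps the sponsor unblinded in the patient parts so that patient and healthy exposure can be compared as data arrive.

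Dose and population are also unbalanced. The 0.5 mg/kg cohort, which has the most leverage on the slope, is healthy-only. CG subjects are at 5 and 20 mg/kg, with D3 undecided up to 40. The Extension starts at 20 mg/kg, and any second cohort must be higher. A population shift can therefore enter the slope or, failing that, the residual variance. At stake is whether a pooled slope and its 90% CI, if reported, mean what they appear to mean.

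**Working it through.** **Inputs from the documents (active subjects).**
- Part A: 6 each at 0.5, 5, 10, 20, 40 mg/kg.
- Part B: 6, 4, 6, 4 at 5, 10, 20, 40.
- Part C: 4 each at 10, 20, 40.
- Part D: 4 each at 5, 20 and D3 (undecided, at most 40).
- Part E: one to three cohorts of 4, doses undecided.
- Extension: 20 mg/kg, up to 12 active (SAP Table 3-7) or 21 (Protocol Table 7). Its only Day 1 PK sample is predose, so it enters multiple-dose pools only.

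**Assumptions.** Patient/healthy exposure ratio R = 1.3 to 1.5, the same for CG and GALK-deficient subjects; log-scale SD 0.3 to 0.5; D3 at 40 mg/kg; true slope 1.

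**Formula.** With x = ln(dose) and z = 1 for patients, the slope bias is ln(R) × g, where g = Sxz / Sxx. Here Sxz = (nH·nP/N) × (mean x in patients − mean x in healthy), and Sxx is the total sum of squares of x.

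**Worked case, Parts A + D.** Mean x is 1.981 in healthy subjects (geometric mean 7.2 mg/kg) and 2.765 in CG (15.9 mg/kg). Sxz = (30 × 12/42) × 0.784 = 6.72 and Sxx = 82.27, so g = 0.082. The bias is 0.262 × 0.082 = +0.021 at R = 1.3 and 0.405 × 0.082 = +0.033 at R = 1.5. At R = 1.5 the average 90% half-width is 0.065 (SD 0.3) to 0.098 (SD 0.5), so the bias is a third to a half of it.

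**Coverage.** Ordinary least squares with a t-based 90% interval, 40,000 simulations per case. With R = 1, coverage is 89.7% to 90.4%, which reproduces the nominal 90%.

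| Pool | n healthy/patient | Geometric mean dose, healthy/patient | Slope bias | Coverage |
|---|---|---|---|---|
| Day 1 A+B+C+D | 62/12 | 10.7/15.9 | +0.010 to +0.015 | about 90% |
| Single-dose A+D | 30/12 | 7.2/15.9 | +0.021 to +0.033 | 82–88% |
| Single-dose A+D+E1 at 20 | 30/16 | 7.2/16.8 | +0.027 to +0.042 | 75–87% |
| Day 1 A+B+C+D, E at 20, 40, 40 | 62/24 | 10.7/22.4 | +0.029 to +0.045 | 63–85% |
| Single-dose A+D, E at 20, 40, 40 | 30/24 | 7.2/22.4 | +0.040 to +0.062 | 46–81% |
| Multiple-dose B+C+D | 32/12 | 15.4/15.9 | +0.003 to +0.004 | 91–95% |
| Same, Extension 12 at 20 | 32/24 | 15.4/17.8 | +0.020 to +0.030 | 90–92% |
| Same, Extension 21 at 20 | 32/33 | 15.4/18.4 | +0.028 to +0.043 | 89–90% |
| Same, Extension 12 at 20 and 9 at 40 | 32/33 | 15.4/22.2 | +0.047 to +0.073 | 72–86% |

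Separate runs differ by up to about one point. The summary range of 62–87% for Day 1 A to D with E at 20, 40, 40 and for the split Extension is rounded outward for that reason. In multiple-dose B+C+D the interval does not miss; at R = 1.5 and SD 0.3 it is too wide, 0.116 against 0.0985 with a population term (about 17%).

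**Dependence on the undecided doses.** With D3 at 10 instead of 40 mg/kg, the A+D bias is at most +0.015 and coverage is 90–93%. Over 28 possible Day 1 layouts with R = 1.5 and CV 40%, median coverage is 91.5% (81% to 94%) and 21% of layouts fall below 88%. Over 84 multiple-dose layouts the median is 91% (69% to 94%), with 31% below 88%.

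**With a population term.** Coverage is about 90% in every row. For R = 1.3 to 1.5 the half-width is narrower or at most about 2% wider, except for A+D with E at 20, 40, 40, where it can be 7% wider. If there is no exposure difference, it is 0 to 5% wider (10% in that same layout).

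**The case against.** The pooled fit is optional and has no listed output. Each part holds one population, so the by-part fits are untouched. The code is offered as an example. No dose decision in Protocol 3.4 or 3.5 uses a pooled slope, no pass/fail limits exist, and patient and healthy exposure are compared directly, so a shift would be visible elsewhere. The first reporting set covers Parts A to D, where the Day 1 pool covers at about 90% and the multiple-dose pool at 91–95%. The lowest coverage figures need several undecided patient cohorts at 40 mg/kg.

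All of this stands, and it keeps the point small. It does not remove it. The near-nominal Day 1 A to D result does not carry over to single-dose AUCinf. SAP Table 6-1 defines that parameter for Part A and the single-dose periods of D and E, while Table 6-2 gives AUCinf for the last dosing day only. Its single-dose pool is therefore A+D, or A+D+E, where coverage falls below 90% with D3 at 40.

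A reader might infer that any population difference will appear as a departure from proportionality, or that the pooled slope is the plan's main statement on proportionality. Neither is supported. The first needs population to be correlated with log dose, and the second is contradicted by the by-part plan and table list.

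**Conclusion.** The point holds in limited form. The pooled model as written lacks a term for a difference that the protocol treats as an open question. Where patient doses sit above healthy doses, the slope is biased upwards if patient exposure is higher (downwards if it is lower), and the 90% CI can under-cover: 82–88% for A+D, 75–87% with E1 at 20 mg/kg, roughly 62–87% in the two main layouts clustered at 40 mg/kg, and 46–81% for the AUCinf pool with Part E at 20, 40, 40. Where doses are similar, coverage is 89–95% and the cost is mainly a wider interval.

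The bias is at most 0.07 on a slope of 1 in these cases, in a descriptive and optional analysis. The exposure ratio, SD and undecided doses are all assumed. The check takes the same ratio for both patient groups and one value per subject; repeated values from subjects who enter several cohorts were not examined. This is a cheap improvement, not a flaw in the planned by-part results.

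**What to change.** Add one sentence to SAP 7.10: any fit that pools healthy subjects with patients includes a fixed effect for population (healthy, CG, GALK-deficient), for example `CLASS POP; MODEL LOGPK = LOGDOSE POP`. Report the common slope with its 90% CI, and show the population-by-log-dose term as a check before quoting a common slope. Alternatively, state that the pooled fit is restricted to healthy subjects.

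The cost is that sentence, one extra model term and one or two degrees of freedom, plus the small change in interval width shown above.
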